## **6.2 Collection and Reporting Requirements for Adverse Events and Serious Adverse Events**

### **6.2.1 Collection of Adverse Events**

All AEs (including SAEs) must be recorded in OnCore® and REDCap (as applicable) and/or an Adverse event log. All AEs required to be collected must be graded according to the CTCAE v5. When possible, signs and symptoms indicating a common underlying pathology should be noted as one comprehensive event. Investigator's or Treating physician's assessment of AE attributions must also be documented.

AEs will be collected from the time the subject signs the consent form through completion of the entire 12-month follow-up period. After this period, investigators should only report SAEs that are attributed to prior study treatment. AEs will be tracked and followed until resolution, subject withdraws consent, or is lost to follow-up (including subjects who discontinue early). All adverse events collected per the protocol will be followed with appropriate medical management until they are resolved, if they are related to the study treatment, or until the investigator deems the event to be chronic.

Please see section 6.2.2 and table 2 to identify the adverse events that need to be reported.

## 6.2.2. Procedures for eliciting, recording, and reporting adverse events

### Eliciting Adverse Events

A consistent methodology for eliciting AEs at all subject evaluation time points should be adopted. Examples of non-directive questions include:

- ☐ “How have you felt since your last clinical visit?”
- ☐ “Have you had any new or changed health problems since you were last here?”

### Specific Instructions for Recording Adverse Events

Investigators should use correct medical terminology/concepts when reporting AEs or SAEs. Avoid colloquialisms and abbreviations.

#### 6.2.2.1 Diagnosis vs. Signs and Symptoms

If known at the time of reporting, a diagnosis should be reported rather than individual signs and symptoms (e.g., record only liver failure or hepatitis rather than jaundice, asterixis, and elevated transaminases). However, if a constellation of signs and/or symptoms cannot be medically characterized as a single diagnosis or syndrome at the time of reporting, it is acceptable to report the information that is currently available. If a diagnosis is subsequently established, it should be reported as follow-up information.

#### 6.2.2.2 Deaths

All deaths that occur during the protocol-specified AE reporting period (see Section I), regardless of attribution, will be reported to the appropriate parties. When recording a death, the event or condition that caused or contributed to the fatal outcome should be reported as the single medical concept. If the cause of death is unknown and cannot be ascertained at the time of reporting, report “Unexplained Death”.

#### 6.2.2.3 Preexisting Medical Conditions

A preexisting medical condition is one that is present at the start of the study. Such conditions should be reported as medical and surgical history. A preexisting medical condition should be re-assessed throughout the trial and reported as an AE or SAE only if the frequency, severity, or character of the condition worsens during the study. When reporting such events, it is important to convey the concept that the preexisting condition has changed by including applicable descriptors (e.g., “more frequent headaches”).

#### 6.2.2.4 Hospitalizations for Medical or Surgical Procedures

Any AE that results in hospitalization or prolonged hospitalization should be documented and reported as an SAE. If a subject is hospitalized to undergo a medical or surgical procedure as a result of an AE, the event responsible for the procedure, not the procedure itself, should be reported as the SAE. For example, if a subject is hospitalized to undergo coronary bypass surgery, record the heart condition that necessitated the bypass as the SAE.

Hospitalizations for the following reasons do not require reporting:

- Hospitalization or prolonged hospitalization for diagnostic or elective surgical procedures for preexisting conditions
- Hospitalization or prolonged hospitalization required to allow efficacy measurement for the study or

- Hospitalization or prolonged hospitalization for scheduled therapy of the target disease of the study

### 6.2.3 Reporting of Adverse Events and Serious Adverse Events

Sponsor-Investigator will be responsible for collecting all protocol-defined Adverse Events (AEs)/Serious Adverse Events (SAEs), pregnancy reports, other Special Situation reports, AESIs and Product Complaints with an AE where the patient has been exposed to the investigational product

Please refer to table 2 below to identify adverse events that meet reporting requirements.

All serious adverse events (SAEs) must also be documented in OnCore® and REDCap.

**Table 2**

Attribution	SAE				AE		
	Grade 1, 2 & 3		Grade 4 and 5		Grade 3	Grade 4	
	Expected	Unexpected	Expected	Unexpected	Unexpected	Expected	Unexpected
Unrelated Unlikely	IRB  and DSMC- Routine Review 	IRB  and DSMC- Routine Review 	IRB  - Routine Review 	IRB  - Routine Review 	DSMC  - Routine Review	DSMC  - Within 5 calendar days	DSMC  - Within 5 calendar days
Possible Probable Definite		IRB  and DSMC  - Within 5 calendar days	DSMC  - Within 5 calendar days	IRB  and DSMC  - Within 5 calendar days			

Guidance on Adverse Event Reporting to the IRB is available online at [MCW IRB Policies and Procedures](#).

For routine reporting, the events will be reported to IRB as part of the annual continuing progress report, and the DSMC will review events entered in OnCore® at the time of scheduled monitoring.

For expedited DSMC reporting, study coordinator/research nurse must notify the DSMC via email. For AEs, include the subject ID, date of event, grade, relatedness, expectedness, and a short narrative. For SAEs, DSMC will review the SAE report entered into OnCore®.

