**Notes:**

a. Instrumental activities of daily living refer to preparing meals, shopping for groceries or clothes, using the telephone, managing money, etc.

b. Examples of self-care activities of daily living include bathing, dressing and undressing, feeding oneself, using the toilet, and taking medications, as performed by patients who are not bedridden.

c. If an event is assessed as a "significant medical event," it must be reported as a serious adverse event.

d. Grade 4 and 5 events must be reported as serious adverse events.

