## 7.2 Objectives and Analysis Plans

### 7.2.1 Primary Objective and Analysis Plan

The primary objective of the study is to determine the safe reduction of the number of fractions (10, 8, or 5), that may be delivered safely in resected HNSCC patients with intermediate pathologic risk features.

The minimum number of safe fractions will be determined as the radiation dose at which there is no more than a 33% rate of dose-limiting toxicity (DLT) up to 12 months after completion of radiation treatment (to allow for the development of late toxicities from radiation treatment) using the TITE-CRM design.

A DLT will be defined for the purposes of this protocol as an inability to complete radiation treatment within 30 days of the start of radiotherapy not deemed to be related to disease progression or unrelated death, unacceptable toxicity within one year of treatment (Grade 4+ toxicity) probably or definitely related to radiation treatment as deemed by the treating physician, or a death within one year of treatment deemed probably or definitely related to treatment. Expected Grade 3 acute toxicities typical of head and neck radiation that resolve within 90 days of treatment, including acute dermatitis, acute mucositis, feeding tube placement, electrolyte abnormalities, pain requiring narcotic medication and dehydration requiring IV hydration will **NOT** be considered DLTs. Grade 4+ late toxicities that may be considered a DLT of radiation include but are not limited to:

- Chondronecrosis of the laryngeal cartilages
- Laryngeal edema requiring tracheostomy
- Carotid blowout syndrome or other life-threatening vascular bleed
- Aspiration pneumonia requiring ICU admission not related to tumor progression
- Chronic non-healing wound or soft tissue necrosis requiring flap reconstruction
- Brainstem necrosis
- Radiation myelopathy

Death deemed unrelated to radiation (such as death due to malignancy or other comorbidity) will not be considered a DLT.

All patients who initiate radiation therapy will be evaluable for the primary endpoint as long as they initiate radiation therapy.

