#### **7.4 Study Monitoring, Interim Analyses, and Early Stopping Rules**

This is a Phase I clinical trial. Patients will receive continued follow-up during and after treatment up to 12 months after completion of the HART-HN regimen. All side effects will be reported and any adverse events will be reported to the IRB as per national and local clinical trial requirements. The project is monitored at all times by the Principal Investigators and/or co-investigators. A physician is present at all exams. The Institutional IRB reviews each project yearly. If at any time during the study, there is a greater than 95% probability that the 12-month of Dose Level 1 exceeds 33%, accrual will be suspended temporarily. Accrual will only resume, if, after further follow-up, this probability is less than 95%.

**Adverse Event Reporting:** Any adverse event such as unanticipated or severe toxicity from radiation would be reported to the IRB under the guidelines as required by our Institution. Any DLT will be reported to the MCW DSMC within 5 calendar days of the study staff's knowledge of such an event.

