### **8.5 DSMC**

The Medical College of Wisconsin Cancer Center places the highest priority on ensuring the safety of patients participating in clinical trials. Every cancer interventional trial conducted at MCW includes a plan for safety and data monitoring.

More information can be found related to the MCWCC Data and Safety Monitoring Plan at the MCWCC website ([Data and Safety Monitoring Plan](#)).

This study will be reviewed by the Medical College of Wisconsin Cancer Center Data and Safety Monitoring Committee (MCWCC DSMC). A summary of the MCWCC DSMC activities are as follows:

- Review the clinical trial for data integrity and safety
- Review all DSM reports
- Submit a summary of any recommendations related to study conduct
- Terminate the study if deemed unsafe for patients

A copy of the MCWCC Data and Safety Monitoring Plan and membership roster will be maintained in the study research file and updated as membership changes. The committee will review reports from the study PI twice annually (or more frequently if needed) and provide recommendations on trial continuation, suspension, or termination as necessary.

Any available DSMC letters will be submitted to the IRB of record as required.

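### Table 2 gives Grade 4-5 SAEs called unrelated or unlikely only routine review, slower than a non-serious Grade 4 AE, so the DSMC may first see a misattributed event after the next dose decision

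*Combined protocol and SAP*

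**What the plan says.** Table 2 in Section 6.2.3 sets the reporting route by seriousness, grade, expectedness and attribution. For events judged unrelated or unlikely:

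- Grade 1-3 SAEs go to the IRB and the DSMC for routine review.
- Grade 4-5 SAEs, expected or unexpected, carry the entry "IRB 1 - Routine Review 2". The DSMC is not named.
- Grade 4 AEs that are not SAEs, expected or unexpected, carry the entry "DSMC 3 - Within 5 calendar days".

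Grade 4-5 SAEs called possible, probable or definite go to the DSMC within 5 calendar days.

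Footnote 2 defines routine review. For the IRB: "For routine reporting, the events will be reported to IRB as part of the annual continuing progress report". For the committee: "the DSMC will review events entered in OnCore® at the time of scheduled monitoring". Section 8.5 gives the schedule: "The committee will review reports from the study PI twice annually (or more frequently if needed".

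Under Section 7.2.1, Grade 4 or higher toxicity is a DLT only if it is "probably or definitely related to radiation treatment as deemed by the treating physician". A death must likewise be probably or definitely related. Section 7.4 adds: "Any DLT will be reported to the MCW DSMC within 5 calendar days of the study staff's knowledge of such an event".

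**The concern.** In a TITE-CRM trial each patient's DLT status feeds the next dose assignment. A Grade 4 event or death that the clinician calls unrelated or unlikely is not a DLT, so that patient's follow-up to that point counts as free of DLT. If the call is wrong, someone outside the study team should be able to question it before more patients are assigned on the strength of it.

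Table 2 gives these events the slowest route it has. The ordering is also hard to explain: for the same attribution, the DSMC is named for Grade 1-3 SAEs and is told within 5 days of a non-serious Grade 4 AE, but is not named for a serious Grade 4 event or a death.

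Within this group the error runs one way. Every event in it has been recorded as a non-DLT, so a late correction can only add DLTs. Until then, the dose level looks safer than it is.

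**Working it through.** The plan states no figure on this point, so the check is first a reading of the routes and then a rough size.

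**1. Where the two cuts fall.** The attribution scale in Section 6.1.4 runs unrelated, unlikely, possible, probable, definite. Table 2 divides it between unlikely and possible. The DLT definition divides it between possible and probable. For Grade 4-5 SAEs:

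- Probable or definite: a DLT; DSMC within 5 days.
- Possible: not a DLT; DSMC within 5 days.
- Unlikely or unrelated: not a DLT; routine review only.

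Only the third group lacks prompt DSMC notice. A true DLT lands there only if it is moved at least two categories, from probable to unlikely.

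**2. Whether another rule closes the gap.**

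- The 5-day DLT notice in Section 7.4 starts only once an event has been called a DLT.
- Section 6.2.2.2 requires deaths to be reported whatever the attribution, but names no recipient and no deadline.
- Section 8.2 has the study team meet regularly to review reportable SAEs and the next subject's intervention. That team is the PI, coordinator, regulatory specialist and biostatistician, so it is not independent.
- Footnote 2 and Section 8.5 give the DSMC sight of the event, but at scheduled monitoring.

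**3. Timing against dose decisions.** Two reviews a year are 12 / 2 = 6 months apart. Under Section 7.1, when three patients enrol rapidly at a new level, enrolment pauses until one has a DLT or at least 3 months pass from the start of their radiation. Three months is shorter than six, so escalation can come before the DSMC sees the event.

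**4. Patients assigned meanwhile.** Section 7.3 gives 3 patients every 2 months, or 1.5 per month; 18 / 1.5 = 12 months reproduces the stated accrual time.

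- 5-day notice: 1.5 × 5 / 30.44 = 0.25 patients.
- Six-month interval, no pause: 1.5 × 6 = 9 patients, half of the 18.
- Six-month interval containing one full 3-month pause: 1.5 × (6 − 3) = 4.5 patients.

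**5. What one call can do to the stopping rule.** Section 7.4 suspends accrual when the probability that the Dose Level 1 rate exceeds 33% is above 95%. The documents give no prior, so this is an illustration with a beta-binomial model and complete follow-up, under assumed Beta(1,1) and Beta(0.5,0.5) priors. The posterior is Beta(a + x, b + n − x) for x DLTs in n patients:

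- 3 of 3: 98.8% and 99.3%, so accrual is suspended. 2 of 3: 89.2% and 88.9%, so it is not.
- 4 of 6: 95.7% and 95.6%, so accrual is suspended. 3 of 6: 83.2% and 81.5%, so it is not.

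In these high-toxicity cases, a single reclassified event switches the rule.

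**The case against.** The strongest reply is that the events nearest the DLT line are already covered. A reader might infer from Table 2 that the judgement defining the primary endpoint has no prompt outside view at all. The documents do not support that: a clinician who hesitates between possible and probable produces an event the DSMC sees within 5 days either way. This stands, and it confines the gap to unrelated and unlikely calls. The DLT for failing to complete radiation within 30 days does not use this attribution scale either.

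Secondly, the DSMC is not excluded. SAEs are entered in OnCore, footnote 2 gives the committee sight of them, and Section 8.5 allows more frequent review. This also stands: the defect is one of timing. The institutional monitoring plan cited in Section 8.5 is not among the documents and may contain further triggers.

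Thirdly, a reader might infer from note d in Section 6.1.3, "Grade 4 and 5 events must be reported as serious adverse events", that the non-serious Grade 4 column is empty. The note is attached to the scale for events not specifically listed in CTCAE, so the column can still apply to listed Grade 4 events that meet no seriousness criterion. The note and the column need reconciling, but the ordering problem in Table 2 does not depend on the note.

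Fourthly, a reader might treat every death as a potential DLT. At the simulated one-year survival of 75.4%, 18 × (1 − 0.754) = 4.4 deaths are expected. Section 7.2.1 excludes deaths due to malignancy or comorbidity, Section 7.1 censors deaths from progression without radiation toxicity at last follow-up, and no split by cause is given. The 4.4 therefore does not measure the problem.

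Finally, the blank lower cells under the AE columns are probably merged cells lost in the text, so nothing is inferred from them. The two SAE cells at issue are legible.

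**Conclusion.** The point holds in a limited form. Grade 4-5 SAEs called unrelated or unlikely have a slower route to independent review than less serious events in the same table, and no other stated rule supplies a prompt independent look. A wrong call of this kind could remain unseen by the DSMC for up to about six months, past the 3-month minimum pause. About 4 or 5 patients could be assigned in that time if one full pause falls in the interval, and at most about 9 with no pause.

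This assumes the planned accrual rate, DSMC reviews six months apart with none added, and an event just after a review. The documents give no misattribution rate, so the chance of this happening cannot be estimated. The stopping-rule figures rest on assumed priors and show only that one event can matter. This is a cheap improvement to safety oversight; it does not show that the primary endpoint is unsound.

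**What to change.** 1. In Table 2, send all Grade 4-5 SAEs to the DSMC within 5 calendar days whatever the attribution, matching the Grade 4 AE column. The IRB entries can stay as they are.
2. Reconcile the Grade 4 AE column with note d in Section 6.1.3. State whether that note applies only to events not listed in CTCAE.
3. Reconcile the treatment of unlikely: the causality guideline in Section 6.1.4 classes it as related, while Table 2 groups it with unrelated.

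The cost is a table edit, two clarifying sentences and a small number of extra DSMC notices by the email and OnCore route already in use. As a guide, the 4.4 expected deaths of any cause imply about four or five notices for deaths, some of which Table 2 would already send. The documents give no rate for non-fatal Grade 4 SAEs called unrelated or unlikely, so that part cannot be counted.

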### 6.2.4 Reporting Instructions

- **Reporting to Regulatory Authorities, Ethics Committees and Investigators**

Sponsor Investigator, as the Sponsor of the Study, will be responsible for the expedited reporting of safety reports originating from the Study to the Regulatory Authorities (FDA) where it has filed a clinical trial

approval, in compliance with local regulations.

Sponsor Investigator, as the Sponsor of the Study, will be responsible for the expedited reporting of safety reports originating from the study to the EMA through Eudravigilance Clinical Trial Module (EVCTM), where applicable.

Sponsor Investigator will be responsible for the expedited reporting of safety reports originating from the Study to the Ethics Committees and Institutional Review Boards (IRB), where applicable.

Sponsor Investigator will be responsible for the distribution of safety information to its own investigators, where relevant, in accordance with local regulations.

### **6.3 Unanticipated Problem Involving Risk to Subject or Other (UPIRSO)**

The investigator and his or her team will follow the Medical College of Wisconsin policies related to unanticipated problems involving risks to subjects or others. This information may be found on the [Human Research Protection Program website](#).

### **6.4 Subject Complaints**

If a complaint is received by anyone on the study staff, it will be discussed with the study staff and will be addressed on a case-by-case basis. The PI will be notified of any complaints. Complaints will be reported to the IRB if indicated.

If the subject has questions about his or her rights as a study subject, wants to report any problems or complaints, obtain information about the study or offer input, the subject can call the Medical College of Wisconsin/Froedtert Hospital research subject advocate at [contact]. This information is provided to the subject in their consent.

Further, if VA subjects have questions about their rights as study participants, they may contact the local VA IRB research subject advocate at [contact], [name]. This information is provided to the subject in their consent form.

## **7 STATISTICAL CONSIDERATIONS**

### **7.1 Study Design**

This is a Phase I dose-hypofractionation trial of radiation dose using a novel radiation treatment regimen called HART-HN. The primary objective of the study is determine the safe reduction of the number of fractions (10, 8, or 5), of the HART-HN regimen, that may be delivered safely in resected HNSCC patients with intermediate pathologic risk features, using the Time-to-Event Continuous Reassessment Methodology design. This will be determined as the radiation dose with the minimum number of fractions at which there is no more than a 33% rate of dose-limiting toxicity (DLT) up to 12 months after completion of radiation treatment (to allow for the development of late toxicities from radiation treatment). There will be three radiation dose levels (all with a BED3 of approximately 100 Gy) evaluated to the operative bed: 42 Gy in 10 fractions (Dose Level 1), 39 Gy in 8 fractions (Dose Level 2) and 32.5 Gy in 5 fractions (Dose Level 3). The total sample size for this study is 18 patients to be recruited over 12 months.

TITE-CRM is an adaptive Phase I trial design methodology which allows for MTD-finding by weighting the follow-up contribution of previously enrolled patients to the selection of the dose level for each newly enrolled patient. If a patient dies of disease progression without evidence of radiation-related toxicity, they will be censored for

toxicity at the time point of last follow-up. Thus, TITE-CRM allows for dose modification even if patients have not completed the entire follow-up period. At the enrollment of each new patient, beyond the three initial patients who will receive the lowest dose of 42 Gy), all available follow-up for all patients already on study will be used to determine the dose level for the newly enrolled patient based on the TITE-CRM methodology. For example, if three patients are enrolled every two months, by month seven, the first patient (who enrolled in month 1) provides up to 6 months of follow-up whereas the ninth patient (who enrolled in month 6) provides only about 1 month of follow-up. All available follow-up data from the first nine patients will be used by the TITE-CRM model to make a decision on the dose for the tenth patient. Unlike a standard 3+3 design, the TITE-CRM model may maintain the current dose level, increase the dose level or decrease the dose level based on all available follow-up data at the time of enrollment of the tenth patient.

To implement the TITE-CRM model, we will be using the `titecrm` function from the R package `dform`. An unconstrained TITE-CRM model potentially allows for rapid early dose escalation from Dose Level 1 to 3. To prevent this overly aggressive dose escalation we will require at least 3 sequential patients at each dose level, prior to escalating dose. Further, in the case of rapid enrollment of 3 sequential patients at a new dose level, enrollment will be paused until one of these patients experiences a DLT or a minimum of 3 months elapses from the initiation of radiation treatment for these 3 patients.

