## STUDY SCHEMA

## STUDY CALENDAR

Study Assessment	Screening	Pre-Intervention*	Intervention**					Follow-up (until 12-months post RT)***			
Procedures	Day -30 to Enrollment	Simulation & Evaluations	RT 1	RT 2-4	RT 5	RT 6-completion	Final Fraction of RT (+/- 48 hours)	2, 4, and 6 wk Post-RT Follow-Up (+/- 7 days)	3 mo Post-RT Follow-Up (+/- 14 days)	6 mo Post-RT Follow-Up (+/- 14 days)	9 and 12 mo Post-RT Follow-up (+/- 14 days)
Informed Consent	X										
Physical Exam (Radiation Oncologist) 	X		X (One visit no later than 24 hours after fraction 5)			X (One visit to be completed no later than 24 hours after final RT fraction)		X	X	X	X
Physical Exam (Surgical Oncologist) 	X								X	X	X
Performance Status	X		X (One visit no later than 24 hours after fraction 5)			X (One visit to be completed no later than 24 hours after final RT fraction)		X	X	X	X
Medical History	X										
Concomitant Medications	X		X (One visit no later than 24 hours after fraction 5)			X (One visit to be completed no later than 24 hours after final RT fraction)		X	X	X	X
AE Assessment	Recorded until completion of the 12-month follow-up period										
Basic Metabolic Panel 	X										
Magnesium (Mg) 	X										
Fasting glucose 	X										
Pregnancy Test 	X										
CT/MR Simulation		X									
Radiotherapy 			X	X	X	X	X				
Radiation Planning		X									
SLP Evaluation		X						X	X	X	X
VFSS Study 		X							X	X	
DIGEST Grade		X							X	X	
FACT- HN Survey		X					X	X	X	X	X
MDADI Survey		X					X	X	X	X	X

Study Assessment	Screening	Pre-Intervention*	Intervention**					Follow-up (until 12-months post RT)***			
Procedures	Day -30 to Enrollment	Simulation & Evaluations	RT 1	RT 2-4	RT 5	RT 6-completion	Final Fraction of RT (+/- 48 hours)	2, 4, and 6 wk Post-RT Follow-Up (+/- 7 days)	3 mo Post-RT Follow-Up (+/- 14 days)	6 mo Post-RT Follow-Up (+/- 14 days)	9 and 12 mo Post-RT Follow-up (+/- 14 days)
Total opioid intake		X					X	X	X	X	X
Visual analog pain scale		X					X	X	X	X	X
Neck CT or MRI and Chest CT or PET/CT of chest 	X								X		

\* Should be completed before starting radiation treatment

\*\* Scheduled as per institutional guidelines and study protocol

\*\*\* If a subject has disease progression/relapse or subject withdrawal, then they will be followed as per follow-up requirements.

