To assess efficacy of the HART-HN regimen assessment of locoregional control and overall survival will be made by the treating radiation oncologist or surgeon at each follow-up, by clinical examination of the head and neck as per the standard of care. Standard post-treatment imaging including a neck CT (with or without contrast) or MRI and a chest CT (with or without contrast) or PET/CT (with or without contrast) will be obtained at 3 months post-treatment (+/- 2 weeks), as per standard of care. Additional surveillance imaging in the follow-up setting has not shown any benefit in 3-year disease-free survival as compared to ongoing clinical surveillance. Therefore, patients will be clinically followed for disease control until locoregional progression, completion of the 12-month follow-up period, patient refusal, or death.

In order to understand the acute and long-term toxicities of the HART-HN regimen patients will be followed clinically by the treating radiation oncologist, undergo routine FACT-HN and MDADI surveys, and undergo scheduled SLP visits including VFSS and DIGEST grading as detailed in the prior section. For the purposes of this study, acute toxicity will be deemed any toxicity that occurs within 90 days of completion of radiation therapy, and late toxicity will be deemed any toxicity that occurs more than 90 days after completion of radiation therapy. During each weekly treatment review and each post-treatment follow-up, the treating physician will record a pain score (scale 1-10) and use the Common Terminology Criteria for Adverse Events Version 5.0 (CTCAE) to record toxicity scores for dysphagia, oral mucositis, dehydration and weight loss. The treating physician will also record tracheostomy tube dependence and feeding tube dependence at each visit.

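### The minimum pause before escalation runs from the start of radiation, so for the last of the three patients it can end 1 to 2 weeks before the target 3-month visit

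*Combined protocol and SAP*

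**What the plan says.** Section 7.1 requires at least three sequential patients at a level before escalation. It adds a pause that applies "in the case of rapid enrollment of 3 sequential patients at a new dose level". The pause ends at the first DLT among those three; failing that, it lasts until "a minimum of 3 months elapses from the initiation of radiation treatment for these 3 patients". The word rapid is not defined. The levels are "42 Gy in 10 fractions (Dose Level 1), 39 Gy in 8 fractions (Dose Level 2) and 32.5 Gy in 5 fractions (Dose Level 3". Outside the pause, "all available follow-up for all patients already on study will be used to determine the dose level for the newly enrolled patient".

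The other clocks start at the last fraction:

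- Section 3.1 schedules visits at 2, 4 and 6 weeks and at 3, 6, 9 and 12 months after completion. The Study Calendar gives the window as "3 mo Post-RT Follow-Up (+/- 14 days"). Nothing is scheduled between 6 weeks and 3 months.
- Section 3.1 also sets the acute/late boundary: "late toxicity will be deemed any toxicity that occurs more than 90 days after completion of radiation therapy".
- Sections 7.1 and 7.2.1 run the DLT window to 12 months after completion, with the stated purpose "to allow for the development of late toxicities from radiation treatment".

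**The concern.** The pause is the only rule that sets a minimum follow-up time before a more condensed level opens, and its clock differs from that of the outcome it protects. A 3-month pause and a 3-month visit sound as if they coincide, but the length of the radiation course separates them.

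Per the Study Calendar, the 3-month visit carries the first post-radiation swallow study with DIGEST grading, the first surveillance imaging and the first surgical examination after radiation. If the pause ends before it, a problem first noticed at that visit in the third patient could come to light after someone has already been assigned the next level.

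**Working it through.** **Inputs.**

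- Pause of at least 3 months from the first fraction, to be met for all three patients (7.1), so the last to start governs. Three calendar months are 89–92 days.
- 10 fractions at Level 1 and 8 at Level 2 (7.1), given daily Monday to Friday (3.1).
- Visits at 6 weeks ±7 days and 3 months ±14 days after completion (Study Calendar).
- Late toxicity begins after day 90 post-radiation (3.1).
- Accrual of 3 patients per 2 months (7.3).

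**The plan's own figures.** Accrual reproduces: 18 / 1.5 per month = 12 months, with no allowance for pauses. The section 7.3 simulation table includes the suspension. It cannot be reproduced because the skeleton, prior variance and arrival process are not given. The calendar check does not depend on it.

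**Step 1. First to last fraction** (any weekday start, no breaks): Level 1, 11–13 days; Level 2, 9–11 days. The lower figure is a Monday start.

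**Step 2. Days post-radiation when the pause ends** = pause length − course length.

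- Level 1: 89 − 13 = 76 to 92 − 11 = 81.
- Level 2: 89 − 11 = 78 to 92 − 9 = 83.

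The first day of late toxicity is day 91, so the third patient is 91 − 81 = 10 to 91 − 76 = 15 days short at Level 1, and 91 − 83 = 8 to 91 − 78 = 13 days short at Level 2.

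**Step 3. Gap to the target 3-month visit.** With a Monday start and 91-day months, the Level 1 visit falls on day 11 + 91 = 102 from the start, 11 days after release. At Level 2 it falls on day 9 + 91 = 100, which is 9 days after. Over every weekday start in 2022–2025, with calendar months, the gap is 9–16 days at Level 1 and 7–14 at Level 2.

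**Step 4. Visit window.** Subtracting 14 days, the earliest permitted visit falls from 5 days before to 2 days after release at Level 1 (9 − 14 = −5; 16 − 14 = 2), and from 7 days before to the day of release at Level 2. An early visit can therefore precede release.

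**Step 5. Age of the 6-week visit at release,** if held on day 42: 76 − 42 = 34 to 81 − 42 = 39 days (Level 1); 78 − 42 = 36 to 83 − 42 = 41 days (Level 2).

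**Step 6. The other two patients.** Two months for three patients is about 20.3 days between starts. With Monday-type courses and a 91-day pause, days post-radiation at release are:

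| | Patient 1 | Patient 2 | Patient 3 |
|---|---|---|---|
| Level 1 | 91 + 40.6 − 11 ≈ 121 | 91 + 20.3 − 11 ≈ 100 | 91 − 11 = 80 |
| Level 2 | 91 + 40.6 − 9 ≈ 123 | 91 + 20.3 − 9 ≈ 102 | 91 − 9 = 82 |

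Patients 1 and 2 then have about 31–33 and 10–12 days of late-period follow-up. All three lack it only if they start within about 90 − 80 = 10 days of each other (Level 1) or 90 − 82 = 8 days (Level 2).

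**Step 7. Effect of a longer pause.** Under section 7.3's constant hazard, and treating the DLT clock as running from the start, P(no DLT in three) = (1 − p)^(3t/365). At p = 0.33 this is 0.67^(273/365) = 74.1% at 91 days, 0.67^(306/365) = 71.5% at 102 days, and 0.67³ = 30.1% at 12 months. TITE-CRM simulations under four assumed skeletons (600 runs each) compared pauses of 3 and 3.4 months. The probability of selecting the true MTD changed by no more than roughly 4 points, about Monte Carlo noise.

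**The case against.** The case for leaving the rule alone is substantial.

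- **The pause is not the only safeguard.** Section 7.1 also requires three patients per level and gives partial follow-up partial weight. With linear weights (an assumption), 91 days counts for about 91/365 = 0.25 of a patient. Section 7.4 has a 95% suspension rule tied to Level 1 and DLT reporting within 5 calendar days. Section 8.2 has the study team review the intervention for the next subject. This stands: the pause is the only *minimum-follow-up* rule, no more.
- **DLTs would surface between visits.** They are Grade 4+ events, treatment-related deaths or failure to complete radiation (7.2.1), and adverse events are recorded continuously. DIGEST is a quality-of-life measure and does not define a DLT. This also stands. A reader might infer that escalation rests on a 6-week examination, but that visit is only the last *scheduled* assessment of one of the three patients.
- **The other two patients are further on.** A reader might infer that the next level opens before any late-toxicity follow-up exists. Step 6 shows this is untrue at planned accrual.
- **A 3-month visit can be on time and still precede release** (Step 4). Only the target date always falls after it.

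What survives is the mismatch of clocks for the patient who sets the pause. The plan gives no reason for it.

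**Conclusion.** The point holds in a limited form. At Levels 1 and 2 the minimum pause can end 7–16 days before the third patient's target 3-month visit and 8–15 days before that patient's late-toxicity period begins. Unless the visit is held early, the 6-week visit is then that patient's last scheduled toxicity assessment. The same mismatch exists at Level 3, but there is no higher level to escalate to.

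The figures assume no treatment breaks, that Level 1 counts as a new level for the pause, and that the pause ends at its minimum. Breaks widen the gap: a course of 30 days, which section 7.2.1 does not count as a DLT, would leave only 89 − 30 = 59 to 92 − 30 = 62 days post-radiation at release.

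The undefined trigger is the other weakness. At planned accrual a fourth patient arrives about 20 days after the third. If that pace is not judged rapid, no pause applies, and the third patient could be about 20 − 11 = 9 days post-radiation at Level 1.

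This is a worthwhile, inexpensive improvement. The documents do not support calling it a failure of the design's safety protection, nor expecting the change to alter MTD selection noticeably.

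**What to change.** In section 7.1, keep the 3-month minimum and the DLT branch and add a second condition:

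> Unless a DLT has occurred in one of the three patients, enrolment resumes at the later of (a) the existing 3-month minimum and (b) entry into the TITE-CRM dataset of the third patient's 3-month post-radiation toxicity assessment. If that visit is missed, or the patient has died, withdrawn or been lost, (b) is met when the visit's +14-day window closes. This applies whenever the three patients at a level have not all met the condition.

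The last sentence replaces the undefined rapid-enrolment trigger. The later-of form matters: tying release to the visit alone could shorten the pause, because an early in-window visit can precede the current minimum. The cap prevents a skipped visit from holding enrolment indefinitely. Re-run the section 7.3 simulations with the revised suspension.

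**Cost.** No extra visits, procedures or patients. The added wait is 9–16 days at Level 1 and 7–14 at Level 2 on target, and at most about 16 + 14 = 30 days per escalation with the window; a course prolonged by breaks would add more. The change secures the 3-month assessment but almost no late-period follow-up: the target visit is 89–92 days after radiation, at most 2 days beyond day 90.
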